9.2. Data collection

Operational data

Operational data regarding the deliverability and supply of blood will be collected on monthly basis from NHSBT and transfusion laboratory.

Clinical data (prospective)

Data will be collected from the clinical team at six sites. Once a case has been identified, the clinical team on each site will be asked to complete the CRF for case using a unique identification number – this will be a sequential number for each site. The completed CRF will be emailed to the central team at Barts Health Trust using nhs.net email accounts.

Study cases will not be contacted or approached for consent and NO identifiers (i.e. names, addresses, dates of birth, hospital or NHS numbers, or date of death) will be sought in the CRF. Respondents will be asked to keep their own record of the unique study number and the patient identifiers in order to facilitate elimination of duplicate reports or raise further gueries if required.

The CRF will be made up of two parts and will seek information as described in Table 1.

Table 1.	Variables that will be collected on the Case Report Form	
Part 1: At	presentation and within 24 hrs of blood transfusion in pre-hospital	
setting (or emergency department for RLH)		
- Gen	der and age	

- Co-morbidities

- Date of transfusion for RC&Plasma (and RBC and FFP)
- Number of units transfused (or ml/Kg for children)
- Donation number for each RC&Plasma transfused
- Amount of crystalloid/colloid administered in 24 hours
- Severity of injury
- Laboratory results (Haemoglobin, platelet, coagulation tests, lactate results) from scene to ED and within 24 hours
- Patient's blood group
- Blood transfusion requirements in the first 24 hours
- Time of death (in hours) from administration of RC&Plasma (or RBC only, or RBC and FFP), and cause of death
- Transfusion reactions

Part 2: At 30 days, or discharge, or death or transfer to another hospital, (whichever is first)

- Date of discharge
- Thrombotic event (arterial or venous)
- Blood transfusion requirements
- Transfusion reactions
- Number of ventilator free days
- Number of intensive care units-free days
- Hospital length of stay
- Time of death (in days) from administration of RC&Plasma (or RBC and FFP), and cause of death

Retrospective data

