Similar information as described in Table 1 will also be collected for trauma patients who have received RBC transfusion in the pre-hospital setting in London between March 2015 to April 2018. Cases will be initially identified from transfusion laboratories at RLH, and once the case has been identified other sites will be asked to submit anonymised clinical information on identified cases using patient's clinical notes and patient's electronic data.

Each case will be given a unique identifier, and no patient's identifier will be collected on the CRF or transferred to the central team at Barts Health.

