10.2. Method of analysis

Statistical analyses will be performed using STATA (StataCorp, USA). Categorical variables will be tabulated as frequencies and percentages and compared using Fisher's exact tests; continuous variables will be summarised as means [standard deviation] or medians [interquartile range] and compared using t-tests or non-parametric equivalents. All tests will be two-sided at the 5% level of significance. Multivariable regression models will be used to examine the association between treatment groups (RC&Plasma versus RBC-only transfusions) and various clinical outcomes, controlling for potential confounders (including but not limited to: type and location of injury; age; other co-morbidities) as appropriate.

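### Section 10.2 promises adjustment for type and location of injury, but Table 1 lists neither among the variables to be collected

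*Protocol*

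**What the plan says.** Protocol section 10.2 plans multivariable regression to compare RC&Plasma with RBC-only on the clinical endpoints. On adjustment, it says that the models will be fitted "controlling for potential confounders (including but not limited to: type and location of injury; age; other co-morbidities) as appropriate". That names four confounders: type of injury, location of injury, age and co-morbidities. The list is open-ended.

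Section 9.2 fixes the data. It states: "The CRF will be made up of two parts and will seek information as described in Table 1". The table is headed "Variables that will be collected on the Case Report Form". Part 1 includes gender and age, "Co-morbidities" and "Severity of injury". The last is the only entry that describes the injury, and no scale is given for it. Part 2 covers discharge, thrombosis, transfusion, organ-support and death data, and has no entry describing the injury.

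For the historical cohort, section 9.2 says: "Similar information as described in Table 1 will also be collected for trauma patients who have received RBC transfusion".

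**The concern.** The RC&Plasma versus RBC-only comparison is a before/after comparison. The London service used RBC in the retrospective window (March 2015 to April 2018) and changes to RC&Plasma from June 2018, so treatment and calendar period coincide. Section 7.1 also words entry differently for the two cohorts. The RC&Plasma cohort requires haemorrhagic shock and major haemorrhage protocol activation. The RBC cohort is defined by having been transfused RBC. Case mix may therefore differ, and regression is the only safeguard that the protocol states.

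If injury type or body region shifts between the periods and also affects base deficit, transfusion requirement, length of stay or survival, a model without those variables may attribute part of the shift to the component. A statistical analysis plan can choose among covariates, but it cannot adjust for variables that were never collected. The mismatch therefore has to be settled in the protocol and the data collection form.

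**Working it through.** **1. Named confounders set against Table 1**

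| Confounder named in section 10.2 | Entry in Table 1, Part 1 or 2 |
|---|---|
| Type of injury | none |
| Location of injury | none |
| Age | listed (Part 1) |
| Co-morbidities | listed (Part 1) |

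Two of four have no entry. Severity of injury is the reverse case: it is collected but not named in section 10.2, although the open-ended list allows it. No other section provides for collecting type or location, and the metrics in section 10.4 do not include them.

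**2. Does severity stand in for them?** Not as written. No instrument is named. A single total grade would give neither mechanism nor body region. A score built up by body region could give location if its components were kept, but the protocol does not say so.

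**3. Both arms of the model.** The retrospective extraction follows Table 1 in similar form, so the gap is likely to affect both groups. The word used is similar, not identical, so the extraction could include more.

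**4. Could the data be recovered later?** Under sections 9.1 and 9.2 the central team receives no patient identifiers, so it has no stated means of linking to another source. Sites do keep their own link between study number and patient, partly so that queries can be raised. Recovery is possible, but only by going back to each site for each case.

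**5. The protocol's own power figure.** Inputs from section 10.1: 160 RBC and 60 RC&Plasma patients, 70% against 50% with base deficit >6 mEq/L. From section 10.2: two-sided 5%.

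- Pooled proportion = (160 × 0.70 + 60 × 0.50)/220 = 0.645
- Standard error under the null = √[0.645 × 0.355 × (1/160 + 1/60)] = 0.0724
- Standard error under the alternative = √(0.70 × 0.30/160 + 0.50 × 0.50/60) = 0.0740
- Power = Φ[(0.20 − 1.96 × 0.0724)/0.0740] = Φ(0.784) = 78.4%

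This agrees with the stated 80% to within 2 points. It is an unadjusted calculation and does not depend on the present point.

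**6. Scale of possible bias, on assumed inputs only.** For an unadjusted comparison, the bias from one binary factor is the difference in its prevalence between periods times its risk difference. The documents give neither. Assumed ranges of 10 to 20 points and 10 to 25 points give:

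- low: 0.10 × 0.10 = 0.01, or 1 point
- high: 0.20 × 0.25 = 0.05, or 5 points

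The effect that section 10.1 targets is 20 points. The formula ignores whatever adjustment for severity, age and co-morbidities would remove, so it illustrates scale and does not estimate residual bias.

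**The case against.** The strongest reply is that the CRF itself is not shown and Table 1 is a list of broad headings. Injury details might sit under severity, and the retrospective data need only be similar to Table 1. This stands as a limit: the documents show that Table 1 does not list type or location, not that the final form omits them.

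A reader might infer that the comparison cannot be adjusted as planned. The documents do not support that. Sites work from clinical notes, keep the link to the patient and can be queried. Severity, age, gender and co-morbidities can enter the model in any case, and severity may absorb part of a shift in injury mix.

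A reader might also take type and location to be the most important confounders because they come first. Section 10.2 does not rank its list, and it qualifies the adjustment as to be made where appropriate. That qualification lets the analyst choose among covariates but does not supply missing ones.

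Finally, this is a feasibility cohort. The primary endpoints in section 6.3 are delivery and wastage, and none of the progression criteria in section 10.3 depends on an adjusted clinical comparison. That stands and limits the priority of the point. It does not remove the inconsistency between the two sections.

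**Conclusion.** The point holds as an inconsistency between the planned analysis and the planned data. On the dataset described in Table 1, the secondary adjusted comparison of RC&Plasma with RBC-only would omit two of its four named confounders unless sites were queried again. The result is avoidable residual confounding of unknown size. The illustrative 1 to 5 points rests wholly on assumed inputs and should not be read as an estimate. The primary feasibility endpoints and the stated power are unaffected. The conclusion assumes that the CRF follows Table 1, as section 9.2 says it will. Priority is moderate.

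**What to change.** Add two items to Table 1 Part 1: type or mechanism of injury, and location of injury (main body region). Apply them to the RC&Plasma cohort and the retrospective RBC extraction, and to the RBC and FFP cohort if that comparison is also to be adjusted. Name the severity scale. Enter type, location and severity in the section 10.2 models with age and co-morbidities.

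If type and location cannot be collected, amend the list in section 10.2 to match Table 1 and state the residual confounding as a limitation of the before/after comparison.

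The cost is two extra items per case, abstracted from notes that sites already use to complete the form, with no patient contact. It is lowest if the change is made before extraction begins, because later recovery means returning to every site.

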10.3. Criteria for progression

Feasibility objectives and related data to be collected	Go criteria to proceed to full trial (Eldridge, et al 2016)	Criteria to reassess and adjust full trial protocol (Eldridge, et al 2016)	Stop criteria (Eldridge, et al 2016)	Rationale
Component Wastage				
i) Rate of component wastage	≤8% wastage	9% - 30% wastage	>30% wastage	On average RBC wastage is 2.5%. With the shorter shelf life of RC/Plasma at 14 days it was decided that 8% wastage would be the acceptable limit Monitored on a weekly basis. Reason for wastage will be documents
Stock Management				
ii) Days without component in the lab (per year)	0 -5 days	6 - 15 days	>15 days	Ideally for the study to work and to assess feasibility of using this component there should be 0 days with no component. Monitored on an monthly basis.
iv) Number of components being transferred to ED on day 10	90% -100% of units	70-89% of units	<70% of units	Monitored on a weekly basis.
Clinical Factors				
v) Number of components used inappropriately in ED to	0% - 5% of units	5 -20% of units	>20% of units	In 2016 of the Incorrect blood components transfused 20% were

Feasibility objectives and related data to be collected	Go criteria to proceed to full trial (Eldridge, et al 2016)	Criteria to reassess and adjust full trial protocol (Eldridge, et al 2016)	Stop criteria (Eldridge, et al 2016)	Rationale
non-trauma, non-bleeding patients				the wrong component and of that 10% were given by the clinical team.
vi) Number of components used inappropriately in ED to non-trauma, but bleeding patients	≤ 10% of units.	10 -25% of units	>25% of units	Monitored on a weekly basis.
vii) Number of patients who received >4 units of RBC/ Plasma component	≤ 2% of patients	3 -10% of patients	>10% of patients	Monitored on a weekly basis.

ED: emergency department

10.4. RC&Plasma metrics

NHSBT
Nr units produced (p.a)
Stock outage (p.a.)
Delivered on time (%)
Delivered in full (%)
Substitutions n / annum (%)
Ad hoc deliveries n / annum
Reduced operator hours (whole supply chain) n / annum
Additional operator hours expended n / annum
Administration costs £/unit
Total cost of delivery £ / unit
Adverse impact on other processes
Beneficial impact on other processes
Adverse impact on other components
Beneficial impact on other components
Adverse impact on testing and QM
Bank holiday management issues
Wastage n /annum
RLH
Nr unit transfused (p.a.)
Nr unit transfused Pre-hospital
NR unit transfused ED (% / p.a.)
Nr unit wasted (% / p.a.)
Nr unit wasted lab (% / p.a.)
NR unit wasted clinical area (n / p.a.)
Inappropriate use (n / p.a.)
Impact on other component
Transport cost
Bank holiday management issues
Pre-hospital setting
Time on scene

11. Ethics

The study will be conducted in compliance with the approved protocol, the Declaration of Helsinki the Principles of Good Clinical Practice (GCP), European

Commission Directive 2005/28/EC with the implementation in national legislation in the UK by Statutory Instrument 2004/1031 and subsequent amendments, the UK Data Protection Act, the UK Policy Framework for Health and Social Care Research (V 3.3, 07/11/2017) and any other applicable national regulations.

The primary ethical and management issues surrounding the proposed study are adequate data protection. In order to address this, we will only collect anomymised data and, the investigators will allocate each case a unique reference number. This number will be shared with the clinical team at other sites and will be used for all subsequent data collection, storage, and transfer.

The primary study database (MS Access) will be stored on a password-protected computer at Barts Health NHS Trust (in the office on the 4th floor of the Pathology and Pharmacy Building at The Royal London Hospital) and will be analysed by the study statistician at Queen Mary University of London: these locations are restricted to Trust haematology staff and academic staff respectively. The study database will be encrypted using the Windows XP Encrypting File System (EFS). Separate back-ups of the study database and the reference number key will be performed weekly using two storage drives stored in secure, fire-proof locations within the building.

The data will be accessible only by the key members of the working group, who may require access to data to ensure compliance with regulations. Access by any other individuals for the purposes of any other study will only be allowed after a successful application to a Research Ethics Committee.

13.1. Data management

The team will consist of study co-investigators and statistician. Study investigators will have access to the central database, which will not contain any patient identifiers. The chief investigator will ultimately oversee and ensure study adherence with appropriate NHS guidelines.

Upon online receipt of the anonymised information of data collection forms via a Secure Sockets Layer (SSL) 128-bit encrypted, password-protected server, the investigators will allocate each participant a unique reference number. This number will be shared with the clinical team at other sites and will be used for all subsequent data collection, storage, and transfer.

The primary study database (MS Access) will be stored on a password-protected computer at Barts Health NHS Trust (in the office on the 4th floor of the Pathology and Pharmacy Building at The Royal London Hospital) and will be analysed by the study statistician at Queen Mary University of London: these locations are restricted to Trust haematology staff and academic staff respectively. The study database will be encrypted using the Windows XP Encrypting File System (EFS). Separate back-ups of the study database and the reference number key will be performed weekly using two storage drives stored in secure, fire-proof locations within the building.

The data will be accessible only by the key members of the working group, who may require access to data to ensure compliance with regulations. Access by any other individuals for the purposes of any other study will only be allowed after a successful application to a Research Ethics Committee.

13.2. Source Data

Data will be collected from the clinical team at six sites using patient's clinical notes and electronic patient records. Once a case has been identified, the clinical team on each site will be asked to complete the CRF for case using a unique identification number – this will be a sequential number for each site. The completed CRF will be emailed to the central team at Barts Health Trust using nhs.net email accounts.

Study cases will not be contacted or approached for consent and NO identifiers (i.e. names, addresses, dates of birth, hospital or NHS numbers, or date of death) will be sought in the CRF. Respondents will be asked to keep their own record of the unique study number and the patient identifiers in order to facilitate elimination of duplicate reports or raise further queries if required.

13.3. Confidentiality

13.3.1. Participant confidentiality

In order to maintain patient confidentiality, no identifiable information will be collected as outlined above. The clinical team will not seek to collect any names, dates of birth, addresses, hospital or NHS numbers in order that none of the participants are individually identifiable.

13.4. Record retention and archiving

The research data will be archived for 20 years according to Queen Mary University of London/ Barts Health NHS Trust policy. The data will be archived in the Modern Records Facility, [name]

14. Safety reporting

Due to the nature and design of this study, safety reporting of adverse events will not occur. Patient will be monitored and treated as part of routine care, and hospital staff will be responsible for reporting all transfusion related adverse events to Serious Hazzard of Transfusion and Serious Adverse Blood reactions and Events according to standard procedures, as required under the regulations of the EU Blood Directive.

15. Monitoring and auditing

The Sponsor or delegate retains the right to audit any study, study site or central facility. In addition, any part of the study may be audited by the funders where applicable.

16. Study committees

This is an observational study that will collect anonymised data on patients who have been transfused blood for management of traumatic haemorrhage. As such, the study does not require any data monitoring/steering/safety committees set up

The study will be managed by the management group below, with the CI overseeing the whole study.

NHSBT

Director of Component Development Laboratory
Supply Chain Specialist
Manufacturing Development
Component team
Head of Manufacturing and Product
Hospital Services
Customer Services

[name]	Continuous Improvement Team
[name]	Component team (CI)

The Royal London Hospital

Trauma Surgeon
Trauma Surgeon
Haematologists (CI)
Transfusion laboratory manager
Transfusion Practitioner
Consultant for Emergency Medicine

The study management group will work closely with PIs, patient and public and other collaborators to ensure that the study meets its objectives.

17. Finance and funding

This study is funded jointly by Barts Charity and London Air Ambulance. A full time equivalent Band 6 researcher assistant will be employed for 2 years to co-ordinate the data collection and cover other administrative tasks

A band 7 scientist (0.4 whole time equivalent) will support the data collection for the transfusion laboratory at RLH – this post is funded by the haematology department at Barts Health Trust.

NHS Blood and Transplant has agreed to ensure a component price for the product to be used in the above study equivalent to a cost saving of £50 for every 'red cell and plasma' unit issued to the Royal London Hospital as part of the study. It is anticipated that around 1,500 units will be used during the study period, equating to an effective grant of £75,000.

18. Insurance and indemnity

It provides cover for the design, management, and conduct of the study.

The Joint Research Office has arranged for suitable indemnity concerning negligent harm to be in place for this study. The insurance that Queen Mary University of London has in place provides "No Fault Compensation" for participants which provides an indemnity to participants for non-negligent harm.

19. Dissemination of research findings

The data from this study will be analysed and the results published as soon as possible in a scientific journal after study completion. The information will be published and distributed to all participating clinicians, as well as being presented at scientific meetings.

20. References

[NG39], N.g. (2016) Major trauma: assessment and initial management. https://www. nice. org. uk/guidance/ng39/chapter/Recommendations-for-research.

- Campbell, H.E., Stokes, E.A., Bargo, D.N., Curry, N., Lecky, F.E., Edwards, A.,
 Woodford, M., Seeney, F., Eaglestone, S., Brohi, K., Gray, A.M. & Stanworth,
 S.J. (2015) Quantifying the healthcare costs of treating severely bleeding
 major trauma patients: a national study for England. *Crit Care*, **19**, 276.
